8.1 ELIGIBILITY CRITERIA

Patients must meet all eligibility criteria:

1. Must have signed informed consent prior to any study-related evaluation
2. Must be male or female patients over 18 years of age
3. Must have unresectable HCC confirmed by histology or by non-invasive AASLD¹⁰ criteria
4. Must have measurable disease defined as at least one uni-dimensional measurable lesion by CT or MRI (according to RECIST 1.1)
5. Must have a Child Pugh score \leq 7 points
6. Must have an ECOG Performance Status score of \leq 1
7. Must have a Life expectancy of 12 weeks or more
8. Must have be eligible to receive SOC sorafenib
9. Must have Platelet count $> 50 \times 10^9/L$ or $> 50\%$ prothrombin activity
10. Must have Hemoglobin $\geq 8.5 \text{ g/dL}$
11. Must have Bilirubin $\leq 2.5 \text{ mg/dL}$
12. ALT and AST must be $< 5X$ upper limit of normal
13. Amylase or lipase must be $\leq 2X$ upper limit of normal
14. Serum creatinine must be $\leq 1.5X$ upper limit of normal
15. INR must be ≤ 2.0
16. Must not have main PVT (branch portal vein thrombosis is permissible)
17. Must not be eligible for curative treatment (e.g ablation or transplantation)
18. Must not have a history of previous or concurrent cancer other than HCC unless treated curatively 5 or more years prior to entry
19. Must not have confirmed presence of extra-hepatic disease with the exception of lung nodules and mesenteric or portal lymph nodes $\leq 2.0 \text{ cm}$ each
20. Must not be at risk of hepatic or renal failure

21. Must not have tumor replacement $\geq 70\%$ of total liver volume based on visual estimation by the investigator OR must not have tumor replacement $\geq 50\%$ of total liver volume in the presence of albumin $< 3 \text{ g/dL}$
22. Must not have any history of severe allergy or intolerance to contrast agents, narcotics sedatives or atropine that cannot be managed medically
23. Must not have any contraindications to angiography and selective visceral catheterization
24. Must not have history of organ allograft

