6.4.2 Secondary Efficacy Variables

The secondary efficacy endpoints for this study are:

- Tumor Response, defined as Objective Response Rate (ORR) according to RECIST v1.1 criteria by investigator determination
- Time to Progression (TTP) according to RECIST v1.1 criteria by investigator determination
- Quality of Life Assessments
- Time to Untreatable Progression (TTUP)

- Time to Symptomatic Progression (TTSP)

6.4.2.1 Objective Response Rate (ORR) according to RECIST v1.1 criteria by investigator determination

Tumor Response is based on the radiological tumor assessment performed at specified time points. The post baseline assessments are compared to the baseline assessment and the overall response based on investigator assessment according to RECIST criteria v1.1 is recorded at each efficacy visit. The tumor response for target lesions is categorized as Complete Response (CR), Partial Response (PR), Stable Disease (SD), Progressive Disease (PD) or Not all Evaluated (NE) according to the RECIST criteria v1.1² as shown in Table 4. Table 5 shows the responses for non-target lesions.

Table 4: Target lesion response categories

Response	Definition
Complete Response (CR)	Disappearance of all target lesions
Partial Response (PR)	$\geq 30\%$ decrease in the sum of the diameters of target lesions
Stable Disease (SD)	Neither CR nor PR nor PD
Progressive Disease (PD)	$\geq 20\%$ increase in the sum of the longest diameter of target lesions from smallest value on study The sum of diameters must also demonstrate an absolute increase of at least 5 mm, e.g. two lesions increasing from 2 mm to 3 mm does not qualify
Not all Evaluated (NE) ^a	When imaging/measurement is not done at all at a particular time point, the patient is not evaluable (NE) at that time point. If only a subset of lesion measurements is made at an assessment, usually the case is also considered NE at that time point, unless a convincing argument can be made that the contribution of the individual missing lesion(s) would not change the assigned time point response.

Source: Protocol version 7.0, 22-Jul-2019; ^aSource: Eisenhauer et al (2009)²

Table 5: Non-target lesion response categories

Response	Definition

CR	Disappearance of all non-target lesions All non-target lymph nodes must be non-pathological in size (<10 mm short axis)
Non-CR/Non-PD	Persistence of 1 or more non-target lesions
PD ^a	Unequivocal progression of existing non-target lesions

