Not Evaluable (NE) ^a	When no imaging/measurement is done at all at a particular time point, the patient is not evaluable (NE) at that time point. If only a subset of lesion measurements are made at an assessment, usually the case is also considered NE at that time point, unless a convincing argument can be made that the contribution of the individual missing lesion(s) would not change the assigned time point response.

^a According to Eisenhauer et al (2009)² “to achieve ‘unequivocal progression’ on the basis of the non-target disease, there must be an overall level of substantial worsening in non-target disease such that that, even in presence of SD or PR in target disease, the overall tumor burden has increased sufficiently to merit discontinuation of therapy. A modest ‘increase’ in the size of one or more non-target lesions is usually not sufficient to qualify for unequivocal progression status.”

Source: Eisenhauer et al (2009)²

Table 6 provides a summary of the overall response status calculation at each timepoint.

Table 6: Timepoint response

Target lesions	Non-target lesions	New lesions	Timepoint response
CR	None	No	CR
PR	None	No	PR
SD	None	No	SD
PD	None	No	PD
Any	None	Yes	PD
CR	CR	No	CR
CR	Non-CR/Non-PD	No	PR
CR	Not evaluated	No	PR
PR	Non-PD or not all evaluated	No	PR
SD	Non-PD or not all evaluated	No	SD
Not all evaluated	Non-PD	No	NE
PD	Any	Yes or No	PD
Any	PD	Yes or No	PD
Any	Any	Yes	PD

None	CR	No	CR
None	Non-CR/Non-PD	No	Non-CR/Non-PD
None	Not at all evaluated	No	NE
None	Unequivocal PD	Yes or No	PD
None	Any	Yes	PD

Source: eCRF

The best overall response is based on the overall responses from each imaging assessment according to RECIST 1.1. It is the best response a patient has had following randomization, but up to and including the first PD or the last valid post baseline imaging assessment in the absence of the first PD.

If a patient received a subsequent systemic anticancer treatment (excluding sorafenib) and/or non-protocol liver directed therapy (excluding ablation/surgery) (henceforth referred to as “subsequent HCC therapy” in this document for ease of reference; see Appendix 4 for details), tumor response assessments after the start date of the subsequent HCC therapy will be excluded from the calculation of best overall response.

The ORR is defined as the proportion of randomized patients achieving a best overall response of CR or PR.

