[figure not shown]
- Dates of collection for laboratory tests (hematology, coagulation, chemistry)
- Date of collection for AFP
- ECOG assessment date
- FACT-Hep assessment date
- Child Pugh Score assessment date
- TheraSphere administration date
- Sorafenib administration start and stop dates
- Date of imaging on Determination of Response eCRF page
- Date of curative treatment on Resection / HCC Stage Migration eCRF page
- Best available care start and end dates on Best Available Care - Post Treatment Discontinuation - Medication eCRF page
- Procedure start and stop dates on Additional Procedures eCRF page
- Date of study exit on Study Exit eCRF page

Sensitivity analysis will be performed to address the poolability of data (See Section 8.6.5).

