11.4 APPENDIX 4: Definition and Derivation of Subsequent HCC Therapy

A patient is considered to have received ‘subsequent HCC therapy’, after the protocol required treatments, if they had

- a subsequent systemic anti-cancer treatment (excluding sorafenib), and/or
- a non-protocol liver directed therapy (excluding ablation/surgery)

Subsequent systemic anti-cancer treatment will be identified using all non-sorafenib records from the “Best Available Care - Post Treatment Discontinuation – Medication” eCRF page. Note that all records on the “Best Available Care - Post Treatment Discontinuation – Medication” eCRF page are expected to be systemic anti-cancer treatments for HCC after data cleaning has been completed.

Non-protocol liver directed therapy will be identified using all records (except ablation/surgery) from “Additional Procedures” eCRF page. This eCRF page captures any procedures relating to liver directed therapies outside the study protocol, such as liver ablation, liver surgery, liver external beam radiation therapy, SIRT with rhenium, SIRT with Y90 (including TheraSphere for patients randomized to control group), TACE, and transarterial embolization (TAE). The free text field “procedure term” will be reviewed and categorized by physician, which will be finalized prior to the database hard lock. Procedures identified as liver ablation and liver surgery by physician’s review will not be considered as subsequent HCC therapy.

Notes:

- Treatments recorded on the “Resection / HCC Stage Migration” eCRF page will not be considered as subsequent HCC therapy, since these treatments are delivered to patients who had a downstaging of disease and represents a population possible to have better outcomes and important to follow-up.
- TheraSphere treatment/retreatment for patients randomized to TheraSphere group, recorded on the “TheraSphere Doses Administered” eCRF page, are study treatment per protocol, so will not be considered as subsequent HCC therapy.

[figure not shown]
**11.5 APPENDIX 5: Statistical Details of the Adaptive Design for Protocol TS-103
STOP-HCC**

Statistical Details of the Adaptive Design

1 Design Overview

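### Scans and AFP values taken after liver surgery or ablation stay in the response endpoints, so a procedure that removes or destroys target disease can be counted as tumor response

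*SAP*

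**What the plan says.** SAP 6.4.2.1 provides that "tumor response assessments after the start date of the subsequent HCC therapy will be excluded from the calculation of best overall response". The same condition governs DCR and the central-review ORR and DCR (SAP 6.4.3.2 to 6.4.3.4), depth of response (6.4.3.9), PTTS (6.4.3.10) and AFP response (6.4.3.11).

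SAP Appendix 4 defines the term. Its liver-directed part is "a non-protocol liver directed therapy (excluding ablation/surgery"). Records on the Additional Procedures page are categorized by a physician; "Procedures identified as liver ablation and liver surgery by" that review are left out, while TACE, bland embolization, external beam radiation and off-protocol Y90 on the same page count. Treatments on the Resection / HCC Stage Migration page likewise "will not be considered as subsequent HCC therapy, since these treatments are delivered to patients who had a downstaging of disease". The reason given goes on to say that this group "represents a population possible to have better outcomes and important to follow-up". No reason is given for leaving out ablation and surgery on the Additional Procedures page.

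The list of OS censoring dates in SAP 8.6.1 shows what the Stage Migration page holds: "Date of curative treatment on Resection / HCC Stage Migration eCRF page". In SAP Table 4 a target-lesion CR is "Disappearance of all target lesions", with no reference to how the lesions disappeared.

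**The concern.** The SAP accepts that non-study local therapy contaminates response, because TACE or radiation ends the response window. It then exempts the procedures that physically remove or destroy the lesion. The stated reason is about following patients who may do well. That supports keeping them in OS; it does not support crediting excision to the randomized arm as tumor response.

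ORR by investigator is a named secondary endpoint, tested at two-sided 0.05 within the hierarchy of SAP 8.6.2, in an open-label trial. The blinded mRECIST versions use the same exclusion rule, so they are no independent check on this point. The listed per-protocol exclusions in SAP 8.3.3 do not name surgery or ablation either.

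**Working it through.** **Tracing one patient through the rules.** The documents state no expected ORR, no power for ORR and no count of procedures, so there is no figure to reproduce. Take a patient with stable disease at Week 16 who is resected at Week 20 and scanned at Week 24.

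1. The resection is not subsequent HCC therapy (Appendix 4), so the Week 24 scan is kept.
2. Best overall response runs to the first PD or, without PD, to the last valid scan (SAP 6.4.2.1), so the scan is inside the window. The exclusion of scans within 6 weeks of randomization (SAP 6.4) does not apply.
3. If the reader records the target lesions as gone, Table 4 gives a target CR. Table 6 then gives CR if non-target lesions are absent or CR and there is no new lesion, and PR if non-target lesions persist or were not evaluated. If only some target lesions are removed, a fall of at least 30% in the sum of diameters gives PR.
4. Depth of response can reach -100%, and the PTTS threshold of a 20% decrease is met at Week 24.
5. If the reader records the removed lesions as not evaluable, none of this follows. Neither document says which applies.

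**Which endpoints move.**
- ORR: only procedures before the first PD, in patients with no earlier CR or PR.
- Depth of response and AFP response: no PD cut-off is stated.
- PTTS: no PD cut-off, but only procedures before the end of the Week 24 window (day 197, SAP Table 3) can matter.
- DCR: the same rule applies, but a patient already scored SD counts anyway, so it moves little.

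**Size, illustration only.** Inputs:
- Patients per arm: 520 planned, 5% assumed ineligible, 1:1 allocation (SAP 4.2, 4.4), so 520 x 0.95 / 2 = 247. Patients without scans stay in the ORR denominator (SAP 6.4.2.1), so the 5% lost to follow-up is not removed.
- Base ORR: assumed 5% to 16%. The upper value is the RECIST response at 90 days in the TheraSphere cohort of 108 patients cited in Protocol 5.3 (10 of 62 evaluated).
- Net excess of patients converted to responders in one arm: assumed 0% to 5%.
- Test: continuity-adjusted Wald (SAP 8.6.2.4), z = (|p1 - p2| - (1/n1 + 1/n2)/2) / sqrt(p1(1 - p1)/n1 + p2(1 - p2)/n2), two-sided 0.05.

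One reclassified patient moves an arm's ORR by 1/247 = 0.40 points. A patient whose depth of response goes from an assumed -10% to -100% moves the arm mean by 90/247 = 0.36 points.

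Two-sided rejection rate with no true difference, by exact binomial enumeration:

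| Base ORR | 0% excess | 1% | 2% | 3% | 5% |
|---|---|---|---|---|---|
| 5% | 3.2% | 5.3% | 11.6% | 22.0% | 50.6% |
| 10% | 3.5% | 4.8% | 8.4% | 14.7% | 34.2% |
| 16% | 3.8% | 4.7% | 7.3% | 11.7% | 26.1% |

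A 2% excess is about 5 patients (0.02 x 247 = 4.9). The 0% column is also the rate after the fix under no true difference; it lies below 5% because of the continuity adjustment.

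**The case against.** The carve-out is deliberate and disclosed: the SAP revision history records both the exclusion rule and its definition. Including the course after downstaging can be defended as a different estimand. Several further points narrow the concern, and they stand.

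- A reader might infer that a resected target lesion **is** scored as CR. The SAP contains no such rule. CR needs all target lesions gone, non-target lesions absent or CR, and no new lesion; the investigator records the response, and not evaluable is an available category. Resecting one of several targets may leave SD.
- Exposure of ORR is limited. Some downstaged patients will already have had a PR and are responders in any case. Entry required that patients "Must not be eligible for curative treatment (e.g ablation or transplantation"), which should keep such procedures uncommon.
- A reader might infer that five such patients suffice for a spurious significant ORR. With 12 against 20 responders of 234 per arm, p = 0.199, and five more in the TheraSphere arm give p = 0.039. That scenario already assumes a true difference and a low base rate. From 12 against 12 of 247, five conversions (12 against 17) give p = 0.44. At a rate nearer 16%, 40 against 48 of 247 plus five (40 against 53) gives p = 0.17.
- ORR is confirmatory only if OS and every earlier endpoint in the hierarchy succeed, and its place is shown in a figure that I could not read. DCR, depth of response, PTTS and AFP response are additional variables outside the named secondary endpoints.

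The gap itself is not answered. No other rule drops these assessments, and the written reason covers only the Stage Migration page and speaks to follow-up, not to attribution of response.

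**Conclusion.** The concern holds in a limited form and is a should-fix. The SAP keeps scans and AFP values taken after liver surgery, ablation and Stage Migration treatments in the response endpoints, has no rule for scoring a removed or ablated lesion, and so allows a procedure to be counted as CR or PR. It treats TACE, external beam radiation and off-protocol Y90 differently without a reason that bears on response.

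Two elements are inference. Transplant is not named in Appendix 4; it is covered through liver surgery and through curative treatment, of which the protocol gives transplantation as an example. A reader might also conclude that the bias certainly favors TheraSphere. That is plausible, because the Stage Migration treatments follow downstaging and the US indication in the protocol synopsis includes neoadjuvant use before surgery or transplantation, but no trial data in the documents show it.

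On the assumed values above, a net 2% excess of conversions raises the rejection rate from about 3-4% to about 7-12%; a 1% excess leaves it close to 5%. The actual size depends on counts that are not given. OS is not affected.

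**What to change.** In SAP 6.4.2.1, 6.4.3.2 to 6.4.3.4 and 6.4.3.9 to 6.4.3.11, exclude assessments after the date of any liver resection, transplant or ablation recorded on the Resection / HCC Stage Migration or Additional Procedures pages, as is already done for other subsequent HCC therapy. Keep any response documented before the procedure. Retain the current rule as a sensitivity analysis, and state there how a removed or ablated lesion is scored. Leave OS unchanged.

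The cost is SAP wording and one more date in the derivation, taken from dates that the eCRF pages already record. The downside is that ORR and the shrinkage measures, and to a small extent DCR, become slightly less favorable in any arm with such patients.

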Appendix

This appendix describes how the lower bound of the promising zone is derived. Let Z_2 and Z_3 be Z-score based on the log rank statistics using the cumulative data at the second look and the last look for the three-look group sequential design with a total of 417 OS events without sample size adaptation. Let c_3 be the efficacy boundary of the group sequential design at the last look. Let Z_3^* be the Z-score based on the actual events at the final look for the adaptive design where the total number of events is increased to 564 for any observed z_2 . Let c_3^* be the adjusted boundary which exactly preserves the conditional type I error. The Muller and Shaffer (2001) principle states that the overall type I error will be controlled if the final test boundary of the adaptive design is adjusted such that the final test of the adaptive design preserves the conditional type I error of the group sequential design. The conditional type I error for the group sequential design is $P_0(Z_3 > c_3 | Z_2 = z_2)$. The conditional type I error of the adaptive design with a fixed sample size increase to 564 for any observed z_2 is $P_0(Z_3^* > c_3^* | Z_2 = z_2)$. In other words, the overall type I error is controlled at one-sided nominal level $\alpha = 0.025$ (or two-sided 0.05) as long as c_3^* satisfies the following equation for any z_2 .

$$P_0(Z_3 > c_3 | Z_2 = z_2) = P_0(Z_3^* > c_3^* | Z_2 = z_2) \quad (2)$$

where $P_0()$ denotes that the probability is evaluated under the null hypothesis that the hazard ratio is 1. The left hand side of (2) is the conditional type I error of the group sequential design given that $Z_2 = z_2$ is observed. By Equation (3) in Gao et al (2008), the left hand side of (2) is given by

$$P(Z_3 > c_3 | Z_2 = z_2) = 1 - \Phi\left(\frac{c_3\sqrt{t_3} - z_2\sqrt{t_2}}{\sqrt{t_3 - t_2}}\right)$$

and the right hand side of (2) is the conditional type given by

$$P(Z_3^* > c_3^* | Z_2 = z_2) = 1 - \Phi\left(\frac{c_3^*\sqrt{t_3^*} - z_2\sqrt{t_2}}{\sqrt{t_3^* - t_2}}\right)$$

where $t_2 = \frac{n_2}{4}$ and $t_3 = \frac{n_3}{4}$ are the cumulative information of the log rank statistics at the

second look and the last look for the original group sequential design, $t_3^* = \frac{n_3^*}{4}$ is the cumulative information of the log rank statistic at the last look for the adaptive design. For this trial, $n_2 = 250$, $n_3 = 417$ and $n_3^* = 564$ and $c_3 = 2.093$. Therefore to preserve conditional type I error, c_3^* need to satisfy the following equation

$$\frac{c_3^*\sqrt{t_3^*} - z_2\sqrt{t_2}}{\sqrt{t_3^* - t_2}} = \frac{c_3\sqrt{t_3} - z_2\sqrt{t_2}}{\sqrt{t_3 - t_2}}$$

i.e.

$$c_3^* = \left[\frac{\sqrt{t_3^* - t_2}}{\sqrt{t_3 - t_2}} \sqrt{t_3} c_3 + z_2 \sqrt{t_2} \left(1 - \frac{\sqrt{t_3^* - t_2}}{\sqrt{t_3 - t_2}} \right) \right] \frac{1}{\sqrt{t_3^*}} \quad (3)$$

By Equation (4) in Gao et al 2008, the conditional power given observed treatment effect $\hat{\theta} = \frac{z_2}{\sqrt{t_2}}$ with the initial planned sample size of 417 is given by

$$\begin{aligned} CP_2 &= \Phi \left(\hat{\theta} \sqrt{t_3 - t_2} - \frac{1}{\sqrt{t_3 - t_2}} (c_3 \sqrt{t_3} - \sqrt{t_2} z_2) \right) \\ &= \Phi \left(z_2 \left[\sqrt{\frac{t_3 - t_2}{t_2}} + \sqrt{\frac{t_2}{t_3 - t_2}} \right] - c_3 \sqrt{\frac{t_3}{t_3 - t_2}} \right) \end{aligned}$$

which implies

$$z_2 = \left(\Phi^{-1}(CP_2) + c_3 \sqrt{\frac{t_3}{t_3 - t_2}} \right) \left(\sqrt{\frac{t_3 - t_2}{t_2}} + \sqrt{\frac{t_2}{t_3 - t_2}} \right) \quad (4)$$

We can express the new boundary c_3^* as a function of the conditional power CP_2 by plugging (4) into (3) as follows

$$c_3^* = \left[\frac{\sqrt{t_3^* - t_2}}{\sqrt{t_3 - t_2}} \sqrt{t_3} c_3 + \frac{\Phi^{-1}(CP_2) + c_3 \sqrt{\frac{t_3}{t_3 - t_2}}}{\sqrt{\frac{t_3 - t_2}{t_2}} + \sqrt{\frac{t_2}{t_3 - t_2}}} \sqrt{t_2} \left(1 - \frac{\sqrt{t_3^* - t_2}}{\sqrt{t_3 - t_2}} \right) \right] \frac{1}{\sqrt{t_3^*}} \quad (5)$$

Similarly we can express CP_2 as a function of c_3^*

$$CP_2 = \Phi \left[\left(c_3^* \sqrt{t_3^*} - \frac{\sqrt{t_3^* - t_2}}{\sqrt{t_3 - t_2}} \sqrt{t_3} c_3 \right) \left(\frac{\sqrt{\frac{t_3 - t_2}{t_2}} + \sqrt{\frac{t_2}{t_3 - t_2}}}{\sqrt{t_2} \left(1 - \frac{\sqrt{t_3^* - t_2}}{\sqrt{t_3 - t_2}} \right)} - c_3 \sqrt{\frac{t_3}{t_3 - t_2}} \right) \right] \quad (6)$$

The green line in the following plot shows the behavior of the adjusted boundary c_3^* against the conditional power and z_2 . Note that c_3^* is a decreasing function of the conditional power. The blue line shows the group sequential efficacy boundary $c_3 = 2.093$ at the last look. In (5) or (6), if we set $c_3^* = c_3$, we can find the conditional power such that the blue line and the green line meet each other which gives $CP_2 = 0.41578$ corresponding to $z_2 = 1.516$. Note that for conditional power > 0.41578 (or $z_2 > 1.516$), we have $c_3^* < c_3$. In particular, $c_3^* < c_3$ for conditional power between 0.41578 and 0.8 (or z_2 between 1.516 and 2.033). Thus setting CP_{min} of the promising zone to 0.41578 assures no inflation of the overall study

type 1 error after increasing the sample size of the study.
